## **II. Research Plan and Design**

**A. Study Objectives:** The objective of this study is to understand the abuse liability and resultant toxicant exposure of new and emerging tobacco products in comparison to smokers' usual brand cigarette and to further understand how flavors in e-cigarette products impact abuse liability among menthol cigarette smokers. The current study is not a cessation study and does not aim to induce long-term uptake of the study products. The objective of the study is to test the acute pharmacokinetic profile and acceptability of these products during a 65-minute use period with each product across three to four study visits. African American and white smokers (N = 20) will be recruited and complete three to four in-laboratory sessions in a randomized crossover design.

**B. Study Type and Design:** The proposed study is a randomized crossover trial. Current smokers will be randomized to session order and complete a standardized 10-puff bout (5 minutes) followed by a 60-minute ad libitum session with each product (usual brand cigarette, e-cigarette, heat-not-burn). Throughout each visit, blood will be collected for nicotine analysis via an IV catheter placed in the patient's arm. Blood samples will be aliquoted into two separate vials. One will be analyzed for the current study and one will be placed in a biospecimen repository if participant provides consent for biorepository. Puff topography will be collected passively throughout the session to measure puffing patterns. Participants will complete self-report measures of nicotine withdrawal and craving. Finally, breath samples will be collected to measure changes in exhaled carbon monoxide, a potent lung toxicant, pre- and post-product use. At the final visit, participants will complete a behavioral economics concurrent choice task (see below for description) to behaviorally measure their decisions regarding use of e-cigarettes or HNB products in place of cigarettes. Finally, participants will be contacted by phone 6 months following the conclusion of visit 3 (or study discontinuation) to complete a phone survey. The objective of this survey is to assess for ongoing use of study products and is part of safety monitoring. We have no hypotheses related to the follow-up.

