**C. Sample size, statistical methods, and power calculation**

1. 20 eligible AA and white smokers will be randomized. We will use a 1:1 fashion randomization to product order (combustible cigarette, e-cigarette, heat-not-burn device vs. combustible cigarette, heat-not-burn device, e-cigarette). Randomization will be determined by computer-generated random numbers. Randomization assignments will be placed in sealed envelopes with sequential study ID numbers. After baseline data collection has been completed, the research assistant will select the sequential study ID number to determine the randomization assignment
2. No blinding is involved in the first three study visits. For participants who complete the fourth visit (flavor assessment), participants and research assistants that interact with participants will be blind to flavor (double blind design).
3. Due to the pilot nature of the current study, a primary aim of the study is to collect data for power calculations for a fully powered trial. Therefore, formal power calculations were not conducted. ANOVAs will be conducted to detect within-subject differences between products for all outcomes. A Bonferroni correction will be applied to adjust for multiple comparisons. A paired samples t-test will be conducted to detect differences in outcomes in the e-cigarette flavor assessment.

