**D. Subject Criteria (See Vulnerable Populations appendix, if applicable):**

Participants will be AA and white adult smokers  $\geq 21$  years old. The study will be open to both men and women. We have chosen to focus on AA because their unique smoking profile places them at potentially greater risk for tobacco-related disease and death and because AA smokers are understudied in terms of the potential differential effect of tobacco-related policy among this population.

Women who are pregnant, plan to become pregnant, or are breastfeeding will be excluded from the study because tobacco products will be provided and smoking is associated with low birth weight and premature labor. Children and those  $<21$  years old will be excluded because the minimum age for purchasing tobacco products is 21 years old.

1. Inclusion criteria: Non-Hispanic African American or white/Caucasian,  $\geq 21$  years old, smoke 5-30 cigarettes per day, daily cigarette smoker, smoked at current rate for at least 6 months, interested in trying e-cigarettes and HNB products, not interested in or unable/unwilling to quit cigarette smoking, willing to complete three in-person study visits, willing to have IV catheter placed.
2. Exclusion criteria: Interested in quitting cigarettes in the next 30 days, use of smoking cessation pharmacotherapy in the past 30 days, use of non-cigarette tobacco products in the past 30 days, use of e-cigarettes  $>5x$  in lifetime, use of e-cigarettes  $\geq 4$  of the past 30 days use of HNB products  $>5x$  in lifetime, use of HNB products  $\geq 4$  of the past 30 days, weight  $< 110$  lbs, uncontrolled hypertension (systolic BP  $\geq 180$  or diastolic BP  $\geq 105$ ), pregnant, plans to become pregnant, or breastfeeding, live  $>10$  miles from study site (Fairway CRU), current enrollment in a research study or program that aims to alter tobacco use.
3. Withdrawal/Termination criteria: Participants will be instructed to practice with (and attempt to switch to) each device prior to attending study visits 2 and 3. Participants may be removed from the study if they fail to complete

sufficient practice prior to each study visit. Additionally, participants will present to the lab nicotine deprived (12 hours abstinent) for study visits 1, 2, and 3. If participants present to study visit 1 and eCO is greater than 12 ppm or they report other nicotine use two times, they will be removed from the study.

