#### **A. E. Specific methods and techniques used throughout the study**

1. Laboratory tests: Throughout each visit, blood will be collected for nicotine analysis via an IV catheter placed in the patient's arm. Blood draws will occur during the PK phase of each visit and will be taken at baseline (0 minutes), 5 minutes, 7 minutes, 15 minutes, and post-ad lib portion (may vary by participant depending on how long they choose to use the product). No more than 7 mL of blood will be drawn per draw ( $\leq 35$  mL per visit). Blood will be processed and analyzed for nicotine and cotinine levels. If consent is provided for banking, samples will be banked for possible future analysis.
2. Study Procedures:
  - a. **Initial screening:** The initial screening will review inclusion/exclusion criteria. Those eligible will be scheduled to completely visit within 14 days.

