- f. **Visit three:** Aside from the product being used, the first portion of visit three will closely mirror visits one and two. Participants will complete baseline self-report measures regarding their practice period (product liking/evaluation and preferences). Participants will again complete CO measurement to confirm tobacco/nicotine abstinence. They will complete a PK and ad-lib session identical to visits one and two. Following the PK and ad-lib sessions, participants will have a 1.5-hour washout/rest period in order to bring them to a state of nicotine deprivation. During the washout period, participants will be allowed to watch a movie or listen to music. Participants will then complete a concurrent choice task with their usual brand cigarette, e-cigarette, and HNB device. In the task, participants will earn puffs of the various products by clicking a mouse/keyboard a set number of times. The participants will be free to choose how they allocate the puffs between the available products. For each task, participants can earn up to 20 puffs and the task will last up to 1.5 hours. Puff topography will be measured throughout the task. The objective of the task is to behaviorally measure whether or not participants see the e-cigarette and/or HNB device as an acceptable or preferable substitute for their usual brand cigarette. Participants will be compensated \$100 for visit

three. In addition, participants will earn up to \$50 for completing all study visits (see section III.G.). We anticipate that visit three will last no more than 4.5 hours.

i. **Computer task:** The usual brand cigarette, e-cigarette, and HNB product are all available. Participants will earn puffs of the products by clicking boxes on a computer screen that represent the products. To earn 1 puff of a product, the participant will be instructed that they must click the corresponding box. In order to earn puffs of the e-cigarette or HNB product, they will click the corresponding box 10 times. To test relative demand for their usual brand cigarette, it will be placed on a variable ratio, meaning the number of clicks necessary to earn puffs of the usual brand cigarette will increase with each trial of the task. Once participants earn a puff, they will be given two minutes to have the puff before the next trial begins.

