#### **V. Data Analysis and Reporting**

**A. Statistical and Data Analysis:** See section II.C. above for sample size and power calculations. To determine differences on self-report measures between products, an analysis of variance (ANOVA) will be conducted. Differences in nicotine delivery will be compared across products at each timepoint using similar procedures. Mean differences in puff allocation will be investigated for the computer task.

**B. Outcome:** The primary study endpoint is nicotine delivery. We hypothesize that combustible cigarettes will show the fastest and greatest nicotine delivery, followed by e-cigarettes, and heat-not-burn devices. Further, topography measures will be greatest for cigarettes, followed by e-cigarettes, and heat-not-burn devices. In terms of self report measures of abuse liability, use of cigarettes will be associated with the greatest reduction in symptoms of nicotine withdrawal and craving. Exhaled carbon monoxide will be greatest for cigarettes, followed by heat-not-burn devices and e-cigarettes (no exposure). The primary endpoint of the computerized concurrent choice task is the proportion of puffs allocated to each product. The third aim is exploratory, and we therefore do not have specific hypotheses related to aim three.

**C. Study results to participants:** Study results will not be shared with research participants.

**D. Publication Plan:** We plan to publish results in appropriate tobacco and public health journals such as Addiction, Tobacco Control, Nicotine and Tobacco Research, etc. In addition, results will be presented at regional, national, and international conferences.

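### The state before the visit-three choice task is called deprivation but not checked, and the puff-allocation analysis leaves out which device was used last

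*Combined protocol and SAP*

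**What the plan says.** - **State before the task.** II.E.2.f (visit three) says of the gap between product session and choice task that "participants will have a 1.5-hour washout/rest period in order to bring them to a state of nicotine deprivation". II.D.3 says that "participants will present to the lab nicotine deprived (12 hours abstinent) for study visits 1, 2, and 3".
- **Use before the gap.** II.B describes a "standardized 10-puff bout (5 minutes) followed by a 60-minute ad libitum session with each product". For visit three, II.E.2.f adds: "They will complete a PK and ad-lib session identical to visits one and two". II.E.1 notes that the timing of the post-ad-lib blood draw "may vary by participant depending on how long they choose to use the product".
- **Order.** II.C.1 specifies "1:1 fashion randomization to product order (combustible cigarette, e-cigarette, heat-not-burn device vs. combustible cigarette, heat-not-burn device, e-cigarette". On method it says: "Randomization will be determined by computer-generated random numbers". Blocking is not mentioned.
- **Analysis.** V.A says: "Mean differences in puff allocation will be investigated for the computer task". II.C.3 plans within-subject ANOVAs by product. V.B makes each product's share of the puffs the primary endpoint of the task. None of these names a sequence or last-device term.
- **Measures around the task.** Arrival CO, the blood draws and the craving/withdrawal ratings all belong to the start of the visit or to the product session. For the task itself, II.E.2.f lists topography only.
- **Visit four.** After a gap of the same length, II.E.2.g calls the interval a washout, makes no claim of deprivation, and collects urge and withdrawal ratings before and after each vaping session.

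**The concern.** The task is meant to show whether smokers would accept either device in place of their own cigarette. How that choice is read depends on the state in which it is made and on what was used just before. The plan gives the state a name that it uses elsewhere for a much longer interval, and it measures nothing that would show which description fits.

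The product used just before the task also differs between the two randomised orders: HNB in one, the e-cigarette in the other. The same device was the one most recently practised with at home (II.E.2.e, 48 hours with up to 3 more days, with encouragement to substitute fully). If recent use changes choice, through satiation or familiarity, allocation reflects that as well as preference. The planned comparison has no means of separating the two. Because II.C.3 makes data for later power calculations a primary aim, an inflated spread would also carry into the next trial's sample size.

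**Working it through.** The plan gives no power or sample-size calculation to reproduce, so the check starts with its timings.

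**1. Timings (II.B, II.E.2.b, II.E.2.f).** 10 puffs x 30 s = 5 min; 5 + 60 = 65 min of access. Visit three: 65 + 90 + up to 90 = 245 min = 4.1 h, within the 4.5 h allowed. The schedule is consistent.

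**2. The two uses of the term.** 1.5 h / 12 h = 12.5%. The documents give no nicotine half-life, so the following is only an illustration. Share of end-of-session nicotine left = 0.5^(t/h):

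| Assumed h | at 1.5 h | at 12 h |
|---|---|---|
| 1 h | 35% | 0.02% |
| 2 h | 59% | 1.6% |
| 3 h | 71% | 6.3% |
| 4 h | 77% | 12.5% |

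Across this range the two intervals leave very different shares. These are shares of an unknown level, however, and say nothing directly about craving or withdrawal.

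**3. E-cigarette minus HNB.** Let D be each participant's difference in allocation, with mean m + r if the e-cigarette was used last and m - r if HNB was. With n1 and n2 participants in the two orders (n1 + n2 = 20), the plain mean of D has bias r(n1 - n2)/20.

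- 10:10: bias 0.
- 12:8: 4/20 = 0.2r. The full difference between sequences is 2r, so this is 10% of it.
- 14:6: 8/20 = 0.4r.

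If the list is unrestricted, with X ~ Binomial(20, 0.5):

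- P(10:10) = 0.18
- P(12:8 or worse) = 0.50
- P(14:6 or worse) = 0.12

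For scale, take r = 0.5 within-sequence SD (an assumption). The bias at 12:8 is 0.2 x 0.5 = 0.10 SD. The standard error is at least 1/sqrt(20) = 0.22 SD, so the bias is under half of one standard error.

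**4. Precision at 10:10.** Ignoring sequence multiplies the SD of D by sqrt(1 + 20r^2/19), with r in within-sequence SDs:

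- r = 0.25: 1.03
- r = 0.5: 1.12
- r = 1.0: 1.43

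Required sample size grows with the square of the SD. At r = 0.5 the factor is 1 + 20 x 0.25/19 = 1.26.

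**5. Cigarette versus device.** Both orders place the cigarette at visit one, so the product used before the task is HNB or the e-cigarette in every participant. No participant is observed with the cigarette as last product. The data therefore contain nothing from which to estimate this contrast free of recent device use, whatever the balance or the model.

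**The case against.** A reader might infer that participants are plainly not deprived when the task begins. The documents do not support that. It would need a half-life and an ad-lib intake that they do not give, and residual nicotine is not the same thing as absence of craving. II.E.2.f also does not claim that 1.5 hours equals 12; the 12 hours is a requirement for arriving at a visit. What remains is one term used for two very different intervals, and no check.

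A reader might also infer over an hour of device use just before the rest. The 65 minutes is access, and actual use varies by participant.

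A third tempting inference is that e-cigarette versus HNB is biased by design. It is not: under 1:1 order an additive last-device effect averages to zero. What is left is chance imbalance and lost precision, and the 0.50 figure holds only if no blocking is used, on which the plan is silent.

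The strongest point against acting is importance. The task serves an exploratory aim in an unpowered pilot, and the study's primary endpoint, nicotine delivery, is collected before the rest and is unaffected. A sequence adjustment also does nothing for the contrast closest to the task's stated purpose, device against cigarette. Both points stand. They lower the importance and mean that the wording of the conclusion has to carry part of the remedy. They do not remove the case for changes that cost almost nothing, especially as visit four already takes comparable ratings after the same interval.

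**Conclusion.** The point holds in limited form and is of minor to moderate importance.

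- II.D.3 and II.E.2.f must be reconciled. Deprivation before the task is unverified; it is not shown to be absent.
- Leaving out the last-used device mainly costs precision in e-cigarette versus HNB. It adds bias only when the orders happen to be unequal, by 0.2r at 12:8. This assumes an additive shift of unknown size r and, for the probability of about 0.50, an unblocked list.
- Cigarette versus device is always measured after recent device use. That follows from the fixed first position of the cigarette and cannot be adjusted away, so it limits what the task can show.

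**What to change.** **V.A.** Estimate the e-cigarette minus HNB difference in puff allocation as the equally weighted average of the two sequence means. Equivalently, fit a product-by-sequence term and average over sequences with equal weight. A sequence main effect alone does not do this, because it leaves the within-person product contrast unchanged. Show allocation to all three products separately for participants who last used the e-cigarette and those who last used HNB.

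**II.E.2.f.** Give the existing craving/withdrawal questionnaire once more, just before the task. CO alone would be a weak check, since the plan itself expects no CO exposure from the e-cigarette (Aim 2, V.B). Describe the state as about 1.5 hours after last product use, and limit the cigarette-versus-device conclusion to choice after recent device use. No change to the length of the rest is proposed.

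**Cost.** One degree of freedom, one short questionnaire and a narrower claim. Equal weighting loses little: at 12:8 the standard error is sqrt((1/12 + 1/8)/4) = 0.228 within-sequence SD, against 0.224 for the plain mean if there were no last-device effect, about 2% more. The pre-task rating has to be taken at the visit, as it cannot be recovered afterwards.

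### The choice task raises only the cigarette's click price, but its endpoint is a pooled puff share with no price term, so a higher device share cannot be read as preference for the device

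*Combined protocol and SAP*

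**What the plan says.** Section II.E.2.f.i (Computer task) sets the prices. For the devices: "In order to earn puffs of the e-cigarette or HNB product, they will click the corresponding box 10 times". For the cigarette: "To test relative demand for their usual brand cigarette, it will be placed on a variable ratio", which the same sentence explains by saying that "the number of clicks necessary to earn puffs of the usual brand cigarette will increase with each trial of the task". On the course of the task: "Once participants earn a puff, they will be given two minutes to have the puff before the next trial begins". Section II.E.2.f gives the limits, "participants can earn up to 20 puffs and the task will last up to 1.5 hours", and the objective, which is to "measure whether or not participants see the e-cigarette and/or HNB device as an acceptable or preferable substitute" for the usual cigarette.

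Section V.B then defines the endpoint: "The primary endpoint of the computerized concurrent choice task is the proportion of puffs allocated to each product". Section V.A gives the analysis: "Mean differences in puff allocation will be investigated for the computer task". Section II.C.3 adds within-subject ANOVAs between products for all outcomes, with a Bonferroni correction whose number of comparisons is not stated. It also says that no formal power calculation was made. Section I.A lists the task under an exploratory aim, with no hypothesis. No section names an analysis by trial or by price, although nothing rules one out.

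**The concern.** Relative demand is choice as a function of price. The task varies the price, and the endpoint then averages over it. Two things follow.

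- The cigarette-versus-device difference reflects both how much smokers want each product and how steeply the cigarette's price was made to rise. The same preferences under two schedules give two different answers.
- The objective covers both *acceptable* and *preferable*. Taking a device once the cigarette has become dear is evidence that the device is acceptable at that price. It is not evidence that the device is preferred.

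At stake is a statement that smokers chose a device over their own brand when the schedule may have produced the result. Because section II.C.3 says that the pilot is to supply data for powering a larger trial, an effect size taken from the pooled share would carry this schedule's influence with it.

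**Working it through.** The documents give no figure to reproduce, so the check asks how far the pooled share can move when preference is held fixed.

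**Inputs from the documents.** Device price 10 clicks; cigarette price rising each trial; up to 20 puffs in up to 90 minutes; two minutes per puff; N = 20.

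**Assumptions.** One puff per trial and 20 trials. The cigarette's start *a* and step *b* are not in the text available, so a range is used. Preference strength, price sensitivity and the form of the test are also assumed.

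**1. Count, with no choice model.** The mildest schedule in whole clicks is 1, 2, ..., 20. Prices 11 to 20 exceed 10, so the cigarette is dearer in 10 of 20 trials. With a start of 10, every trial after the first is dearer: 19 of 20.

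**2. Simple threshold rule.** Take a smoker who picks the cigarette at any price up to twice the device price, that is, up to 20 clicks. The pooled cigarette share is:
- (a, b) = (1, 1): 20/20 = 100%
- (10, 1): prices 10 to 20 qualify, 11/20 = 55%
- (10, 5): prices 10, 15 and 20 qualify, 3/20 = 15%

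**3. Graded choice.** Let the price in trial k be p_k = a + b·k, for k = 0 to 19. Let the cigarette be worth v times each device, and let choice be proportional to value/price^s:

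P_k = v(10/p_k)^s / [v(10/p_k)^s + 2]

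The pooled share c is the mean of P_k, and each device gets (1 − c)/2. Cigarette minus one device is c − (1 − c)/2 = (3c − 1)/2, which changes sign at c = 1/3. With v = 4, the share at equal price is 4/6 = 67%.

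For (10, 5) and s = 1, the first terms are 0.667, 0.571, 0.500, 0.444 and 0.400, and the mean over 20 trials is 0.307. All schedules with s = 1:

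| (start, step) | cigarette share | cigarette minus one device |
|---|---|---|
| (1, 1) | 68% | +52 points |
| (10, 1) | 52% | +28 points |
| (10, 5) | 31% | −4 points |
| (10, 20) | 15% | −27 points |

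The documents' limits do not exclude the steepest of these. Twenty puffs at two minutes use 40 of the 90 minutes. An all-cigarette run costs 20×10 + 20×(0 + 1 + ... + 19) = 200 + 3,800 = 4,000 clicks, which is about 33 minutes at an assumed 2 clicks per second.

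**4. Sensitivity to the choice rule.** With a start of 10 and v = 4, the step at which the sign flips is about 23 clicks for s = 0.5, 4 clicks for s = 1 and 1.3 clicks for s = 2.

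**5. No average preference.** Trials of 20 smokers were simulated with log v normal, mean 0 and SD 0.7, and an assumed paired t-test at 0.05/3.
- Equal prices: significant in under 2% of trials in either direction.
- (10, 1): e-cigarette significantly above cigarette in about 53% of trials (s = 1) or 11% (s = 0.5).
- (10, 1), (10, 5) and (10, 20) with s = 1: cigarette significantly above e-cigarette in 0%.
- (1, 1) with s = 1: cigarette significantly above e-cigarette in about 15%.

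**The case against.** The strongest case on the other side has five parts.

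- **The rising price is deliberate.** It serves the stated demand question and suits the acceptability reading. This stands: the task design is not at fault. The gap is between the design and the endpoint.
- **The result is not meaningless in both directions.** A reader might infer that no significant difference, either way, says anything about preference. That goes too far. If the cigarette never costs less than 10 clicks, a higher cigarette share arises despite the price handicap and is conservative evidence for the cigarette; step 5 shows no false cigarette wins in that case. The ambiguity extends to a higher cigarette share only if the start is below 10, which the text neither states nor excludes.
- **A reversal is not certain.** A reader might also infer that the schedule will overturn a true cigarette preference. Step 4 shows that this depends heavily on price sensitivity, and the largest effect in step 3 needs a cigarette price that ends at 390 clicks. The test at 0.05/3 is likewise an assumption, because the plan names ANOVA with Bonferroni and mentions a paired t-test only for the flavor session.
- **The start and step may exist.** A screen simulation is among the figures not shown, so the plan should not be faulted for leaving them out. Knowing them would fix the schedule but would not put price into the endpoint.
- **The stakes are limited.** The aim is exploratory in a 20-person pilot, and liking and preferences are also collected by self-report. This stands and lowers the weight, although the pooled share is still the named primary endpoint of the one behavioral choice measure.

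**Conclusion.** The point holds in a limited form. Followed as written, the analysis gives a cigarette-versus-device contrast that depends on the price schedule and discards the price information gathered. A higher device share cannot support the claim that the device is preferable. A higher cigarette share remains interpretable if the cigarette always costs at least 10 clicks.

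The firm part is the count of at least 10 dearer trials in 20, which needs only whole clicks, a start and step of at least 1, and one puff per trial over 20 trials. The range of shares from 68% to 15% and the rates of false e-cigarette wins (53% or 11%) illustrate the mechanism under assumed schedules and choice rules; they do not predict this trial's result.

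The documents do not support extending the point to e-cigarette versus HNB, which is at equal price, to the acceptability reading, or to nicotine delivery, the study's primary endpoint. The weight is low to moderate.

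**What to change.** In sections V.A and V.B:

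- Retain the choice and the cigarette price for every trial.
- Report the proportion choosing each product at each cigarette price, and base the cigarette-versus-device analysis on choice as a function of price.
- Compare e-cigarette with HNB directly, at their common price.
- Keep the pooled share as a descriptive measure specific to this schedule, and do not interpret a higher device share as preference.
- State that price is confounded with trial order and satiation in every by-price result, in the display as well as in any model.

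Stating the start and step beside the analysis would help the reader, but it is secondary.

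The cost is a few sentences and the keeping of trial-level records; the task itself does not change. The downside is imprecision. With N = 20 and the 4:1 preference above, the cigarette share at a single 10-click trial averages 65%, and 95% of simulated trials fall between 45% and 85%. The confounding is also real. Under (1, 1) the 10-click price comes at the tenth trial. A 5% loss of cigarette value per trial would then lower the expected share from 67% to 4×0.95^9 / (4×0.95^9 + 2) = 56%.
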